7.3 Disposition of Subjects

A subject disposition summary will be provided. The categories will include all subjects who were enrolled, subjects who were not treated, subjects who discontinued from the study categorized by reason, and subjects who completed the study. The primary reasons for discontinuation will include AE, major protocol deviation, lost to follow-up, study termination, pregnancy, lack of efficacy, voluntary withdrawal, and other.

A summary of screening failures and listings of inclusion/exclusion criteria responses for subjects with violations will also be provided.

7.4 Demographic and Other Baseline Characteristics

Baseline characteristics will be listed and summarized for demographics (sex, age, race, and body mass index), and medical history for the safety analysis set.

Categorical variables will be summarized using frequencies and percentages. Continuous variables will be summarized using mean, SD, median, maximum and minimum values.

7.5 Medical History and Concurrent Medical Conditions

Medical history refers to the significant conditions/diseases that stopped at or prior to signing of informed consent. Concurrent medical conditions are those significant ongoing conditions/diseases present at signing of informed consent.

Medical history and psychiatric history and concurrent medical conditions will be coded using the latest version of Medical Dictionary for Regulatory Activities (MedDRA) and will be

summarized in tables using System Organ Class (SOC) and MedDRA preferred term. The tables will include numbers and percentages of subjects and will be sorted in alphabetical order by system organ class and preferred term. A subject will only be counted once within a particular class even if he/she has multiple conditions/symptoms. Summaries will be based on the safety analysis set.

All medical history and concurrent medical condition data will be presented in listings.

7.6 Medication History and Concomitant Medications

The medication history and concomitant medications are defined as follows:

- Medication history refers to the medication that the study subjects stopped taking within 30 days prior to signing of informed consent (ie, stop date < informed consent date).
- Concomitant medication is defined as medication that the study subjects continued taking or took from signing of informed consent through end of study:
 - Concomitant medication that started and stopped prior to baseline (ie, stop date \geq informed consent date, and stop date \leq first dose date).
 - Concomitant medication that started prior to and was ongoing at baseline (ie, start date < first dose date, and stop date $>$ first dose date) or if coded as ongoing with no stop date.
 - Concomitant medication that started after baseline but before or at last dose (ie, start date \geq first dose date, and start date \leq last dose date).
 - Concomitant medication that started prior to and was ongoing at baseline or that started after baseline (ie, start date \leq last dose date, and stop date $>$ first dose date).
 - If start date and stop date are missing, medication will be assumed to occur both prior and concomitantly.

Medication history and concomitant medications will be coded using the latest version of the World Health Organization (WHO) Drug Dictionary and summarized by giving the number and percentage of subjects by preferred term within each therapeutic class, with therapeutic class and medications in each class sorted in alphabetical order. The total number of subjects with medications in each selected therapeutic class will also be presented. If a subject reports taking 2 drugs belonging to the same class, he/she will only be counted once within that class. Summaries of medication history and concomitant medication will be based on the safety analysis set.

All prior and concomitant medications data will be presented in listings.

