7.1 Inclusion Criteria

Subject eligibility is determined according to the following criteria prior to entry into the study:

- 1. Subject is a man or woman, aged 18 to 65 years, inclusive, and able to read and understand English.
- 2. Subject suffers from MDD as the primary psychiatric diagnosis.
- 3. Subject has been or is currently being treated with an approved antidepressant (monotherapy) for 6 weeks or longer at an adequate therapeutic dose. Subjects currently on an antidepressant at Screening will be discontinued in a manner that is consistent with labeling recommendations and conventional medical practice.
- 4. The subject's antidepressant treatment must be on-going at time of Screening, or have been discontinued within the 6 weeks prior to Screening.
- 5. Subject is considered appropriate for a change in antidepressant medication based on investigator judgment in collaboration with the subject.
- 6. Subject has scores on PHQ-9 \geq 5 and CGI-S \geq 4.
- 7. A female subject of childbearing potential who is sexually active agrees to routinely use adequate contraception* from signing of the informed consent throughout the duration of the study and for 30 days after the last dose of study drug.
- 8. In the opinion of the investigator, the subject is capable of understanding and complying with protocol requirements.
- 9. The subject signs and dates a written, informed consent form and any required privacy authorization prior to the initiation of any study procedures.

*Definitions and acceptable methods of contraception and Contraception and Pregnancy Avoidance Procedure are defined in Section 9.1.9. Pregnancy reporting responsibilities are defined in Section 9.1.10.

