8.1.1.1 Study drug

Vortioxetine is a compound developed by Takeda and H. Lundbeck A/S as an antidepressant and treatment for MDD. Vortioxetine was approved in September 2013 and commercialized in the United States in January 2014. Vortioxetine belongs to a new chemical class of psychotropics, the bis-arylsulfonyl amines, which possess unique properties compared with currently known psychotropics. This class of compounds is structurally different from all currently known psychotropics.

Vortioxetine is commercially formulated as immediate-release tablets intended for oral administration

The study drug will be packaged in high-density polyethylene bottle with child resistant closures. Each bottle contains 28 daily doses plus 7 extra tablets for a total of 35 tablets per bottle to be dispensed at the visits indicated in the Schedule of the Study Procedures (Appendix A). The subjects will be required to take 1 tablet orally, at the same time of day, preferably in the morning, or as directed. The study drug will be labeled with a single label and dispensed as open-label for the 12-week treatment phase. The study drug will be identifiable by a unique identification (ID) number that will be assigned by an IxRT. Each bottle will be labeled with pertinent study information.

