9.1.2 Demographics, Medical History, Medication History, and Disease History Procedure

Demographic information to be obtained will include date of birth, sex, Hispanic ethnicity, race as described by the subject, height, weight, and smoking status of the subject at Screening.

Medical and psychiatric history to be obtained will include determining whether the subject has any significant conditions or diseases relevant to the disease under study that resolved at or prior to signing of informed consent, specifically psychiatric and MDD history as well as previous treatments related to psychiatric and MDD history. Ongoing conditions are considered concurrent medical conditions (see Section 9.1.6). Additionally, the factors for determining a change/discontinuation from the prior antidepressant as assessed by the subject and by the investigator will be collected.

Medication history information to be obtained includes any medication relevant to eligibility criteria and effectiveness/safety evaluation stopped at or within 12 weeks prior to signing of informed consent.

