Appendix A Schedule of Study Procedures

	Screening	Treatment						
	Visit 1 (a)	Baseline Visit 2 (a) Day 1	Visit 3 Wk 2	Telephone Contact Visit 4 Wk 4	Visit 5 Wk 6	Telephone Contact Visit 6 Wk 9	End of Study Visit 7 Wk 12 /Early Termination	Visit 8 Wk 16
	Days -21 up to -1	Day 1	Day 15 (±3 Days)	Day 29 (±3 Days)	Day 43 (±5 Days)	Day 64 (±5 Days)	Day 85 (±5 Days)	Day 113 (± 7 Days)
Informed consent	X							
Eligibility criteria	X	X						
Demographics, medical history, medication history	X							
UDS (b)	X	X						
MDD diagnosis confirmed by investigator judgment, antidepressant medication history & disease history	X							
Height and weight (c)	X	X					X	
Hematology and limited serum chemistry		X					X	
PGx sample collection (d)		X					X	
Concurrent medical conditions	X	X						
Concomitant medications		X	X	X	X	X	X	X
Vital signs	X							
GAS assessment		X			X		X	
PHQ-9	X	X			X		X	
Q-LES-Q		X					X	
PDQ-D		X			X		X	
Company Confidential Inform	ation							
Company Confidential Inforn								
Company Confidential Inforn	nation							
C-SSRS	X	X	X		X		X	
Company Confidential Inforn	nation							
WHO-5		X			X		X	
CGI-S	X	X	X		X		X	
CGI-I			X		X		X	

Footnotes are on last table page.

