Appendix A Schedule of Study Procedures (continued)

	Screening	Treatment						
	Visit 1 (a)	Baseline Visit 2 (a) Day 1	Visit 3 Wk 2	Telephone Contact Visit 4 Wk 4	Visit 5 Wk 6	Telephone Contact Visit 6 Wk 9	End of Study Visit 7 Wk 12 /Early Termination	Visit 8 Wk 16
	Days -21 up to -1	Day 1	Day 15 (±3 Days)	Day 29 (±3 Days)	Day 43 (±5 Days)	Day 64 (±5 Days)	Day 85 (±5 Days)	Day 113 (± 7 Days)
Document factors for determining a change/discontinuation from prior antidepressant (e)	X							
PTE/AE assessment	X	X	X	X	X	X	X	X
Pregnancy testing and pregnancy avoidance counseling (f,g)	X	X	X		X		X	
Access IxRT for subject ID/ medication ID/subject status	X	X	X		X		X	
Dispense study drug		X	X		X			
Dose adjustment (as needed) (h)			X		X			
Clinician and subject satisfaction with change in antidepressant							X	
Clinician and subject satisfaction with GAS approach							X	
Study drug return/accountability/ compliance			X		X		X	

⁽a) Screening and Baseline Visits may be combined as determined appropriate per the investigator. Any procedure that is to be performed at both visits should only be conducted once for a combined visit.

⁽b) UDS to be done at Screening and Baseline. UDS kits will be supplied by the sponsor for the testing at the clinic. UDS results must be negative. This includes benzodiazepines and opiates for which there is no prescription (including oxycodone) at Screening and Baseline. Results must be confirmed prior to conducting the Baseline Visit.

⁽c) Height at Screening only; weight at Screening, Baseline, and Week 12.

⁽d) Subjects who signed an informed consent for PGx testing will have blood samples for PGx analysis and these will be collected as follows: 2×3 mL for DNA on Day 1; 2×2.5 mL for RNA predose on Day 1 and at Week 12 (Visit 6).

⁽e) To be collected at Screening or combined Screening/Baseline Visit.

- (f) Urine hCG pregnancy tests will be performed at Screening and Baseline and for all other visits during the Treatment Period for women of childbearing potential only. Serum hCG pregnancy tests will be performed at Baseline and End of Study/Early Termination visits for all females. For combined Screening and Baseline Visits, there will be 1 urine and 1 serum hCG. Subjects may be enrolled with a negative urine hCG; however, if the serum hCG is positive the subject must be withdrawn from study drug immediately and withdrawn from the study as soon as possible.

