7.7 Study Drug Exposure and Compliance

The summary of study drug exposure and compliance will be based on the safety analysis set.

Duration of exposure to study medication is defined as (date of last dose – date of first dose +1). Treatment duration will be summarized by duration category in weeks (1 to 2 weeks, 3 to 4 weeks, 5 to 6 weeks, 7 to 8 weeks, 9 to 10 weeks, and 11 to >12 weeks) and the number and

CONFIDENTIAL

percentage of subjects in each duration category. Treatment duration (days) will also be summarized using descriptive statistics (n, mean, SD, median, minimum, and maximum).

Percent of study drug compliance is defined as $\{(number\ of\ tablets\ dispensed - number\ of\ tablets\ returned) / (date\ of\ last\ dose - date\ of\ first\ dose + 1)\} \times 100\%$. If a value for the number of returned tablets is missing or the return date is missing, then 100% compliance will be assigned for each day up to the number of tablets dispensed or up to the date of return whichever is earlier.

Study medication compliance will be summarized by compliance category (<80%, 80 to 120%, and >120%) and the number of subjects in each compliance category. Study medication compliance will also be summarized as a continuous variable using descriptive statistics (n, mean, SD, median, minimum, and maximum).

All study drug administration and accountability data will be listed by study site and subject number. The following variables will be listed: subject identifier, visit number, first and last dose dates, medication identification number, date dispensed and returned, number of tablets dispensed and returned, and percent compliance.

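### Does the 30-day medication-history window in SAP 7.6 need to change, given the protocol's 12-week and 6-week windows?

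*SAP*

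**What the plan says.** SAP 7.6 counts as medication history any drug the subject "stopped taking within 30 days prior to signing of informed consent (ie, stop date < informed consent date"). Concomitant medication starts at consent: a drug whose stop date is on or after the consent date belongs there. The section ends: "All prior and concomitant medications data will be presented in listings".

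Protocol 9.1.2 sets what is collected: relevant medication "stopped at or within 12 weeks prior to signing of informed consent". Inclusion criterion 4 in Protocol 7.1 requires the antidepressant to be ongoing at Screening "or have been discontinued within the 6 weeks prior to Screening". Appendix A of the protocol has a separate Screening entry for "antidepressant medication history & disease history".

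On compliance, SAP 7.7 says that when the returned count or return date is missing, "100% compliance will be assigned for each day up to the number of tablets dispensed or up to the date of return", whichever comes first. Protocol 8.1.1.1 gives the pack size: "Each bottle contains 28 daily doses plus 7 extra tablets for a total of 35 tablets per bottle". The "Dispense study drug" row of Appendix A is marked at Baseline, Week 2 and Week 6.

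**The concern.** One SAP bullet holds two rules that disagree for any drug stopped more than 30 days before consent. The narrower one is also shorter than both the protocol's collection window and its antidepressant eligibility window. The study concerns outcome after a change of antidepressant, so a table that omits the drug making a subject eligible would be an awkward gap. Two programmers could produce different tables from the same text. SAP 7.11 gives no reason for a shorter window, and the visible SAP plans no other table of prior antidepressants.

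The compliance rule raises a similar worry. A subject with no tablet returns is credited with a dose a day, which could hide poor adherence, and no planned output counts the imputed values.

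**Working it through.** **Windows in days before consent.** Inputs: SAP 7.6 wording, 30; Protocol 9.1.2, 12 × 7 = 84; Protocol 7.1 criterion 4, 6 × 7 = 42. Consent and Screening are taken as the same day; if consent comes earlier, the eligibility gap shrinks by that many days.

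- Collected but outside the SAP wording: 84 − 30 = 54 days (days 31 to 84), 54/84 = 64%.
- Eligible but outside the SAP wording: 42 − 30 = 12 days (days 31 to 42), 12/42 = 29%.

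**Where a drug falls, by stop date.**

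| Days before consent | SAP wording | SAP date rule | SAP concomitant | Collected (9.1.2) | Meets 6-week limit |
|---|---|---|---|---|---|
| 0 | no | no | yes | yes | yes |
| 1 | yes | yes | no | yes | yes |
| 30 | yes | yes | no | yes | yes |
| 31 | no | yes | no | yes | yes |
| 42 | no | yes | no | yes | yes |
| 43 | no | yes | no | yes | no |
| 84 | no | yes | no | yes | no |

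Three things follow.

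1. Under the date rule no eligible stop date is lost. Days 1 to 84 are medication history, and day 0 is counted once, as concomitant. The rule needs no lower bound of its own, because medication history is collected for only 12 weeks.
2. A drug still in use at consent has a stop date on or after consent, so it is concomitant whichever window is used. The medication-history table was therefore never a full account of what subjects switched from, and widening it would not make it one.
3. The 6-week limit decides who enters and the SAP window decides what is tabulated, so those two differ in scope and do not contradict each other.

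The documents do not say how many subjects were already off drug at consent or when they stopped, so no count of affected subjects can be derived.

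**Compliance.** Assume one 35-tablet bottle per dispensing visit (the number is not stated), each bottle used within its own interval, and no return data. With visits on Days 1, 15 and 43 and 84 days of treatment, the intervals are 14, 28 and 42 days:

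- Imputed compliance = (14 + 28 + min(42, 35))/84 = 77/84 = 91.7%.
- With two bottles at Week 6: 84/84 = 100%.
- Lowest value within the permitted visit windows (visits on Days 12, 38 and 90): (11 + 26 + 35)/90 = 72/90 = 80.0%.
- Week 6 visit missed: (14 + 35)/84 = 49/84 = 58.3%, or 49/70 = 70% if the last dose is on Day 70.

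The cap on tablets dispensed therefore does put some subjects below 80%, and a missed visit is a plausible reason for missing returns.

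**The case for a change.** The best argument for a change is that a listing gives no counts, that collecting antidepressant history at Screening is not the same as planning a table of it, and that a definition should not need interpretation. Correcting the wording would also be cheap, since the data are already collected.

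Part of this stands. The words and the date rule do disagree, and nothing explains the 30 days. But the disagreement has an obvious resolution: the date rule is the part that can be programmed, and it agrees with the protocol's collection period except on the day of consent. Protocol 13.1.1 and SAP 7.2 also provide for Handling Rules for Analysis Data, which may be supplemented and must be final before database lock, so there is a ready place to record the choice.

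On compliance, it is true that a subject with no returns who attends every dispensing visit within window is never imputed below 80% on the one-bottle assumption. It is also true that no table counts the imputations. But SAP 7.7 lists tablets dispensed and returned, both dates and percent compliance by subject and visit, so missing returns can be seen and counted. A second compliance summary would be a preference.

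**Conclusion.** No change to the plan follows. The 30-day wording is a clerical slip. Read literally, it would leave 12 of the 42 eligible off-drug days outside one descriptive table, and only for subjects who had already stopped their antidepressant. Under the date rule in the same bullet the loss is zero, and the listings are complete either way. The compliance imputation is a capped convention whose inputs are listed.

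Both points touch descriptive summaries of the safety analysis set only. SAP 7.8 bases every efficacy analysis on the FAS, so the Week 12 responder proportion and the secondary changes from Baseline are unaffected. The conclusion assumes that consent and Screening fall on the same day and that the programmers follow the date rule. If they followed the words instead, the cost would be an incomplete descriptive table that could be completed from the listings.

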7.7 Study Drug Exposure and Compliance

The summary of study drug exposure and compliance will be based on the safety analysis set.

Duration of exposure to study medication is defined as (date of last dose – date of first dose +1). Treatment duration will be summarized by duration category in weeks (1 to 2 weeks, 3 to 4 weeks, 5 to 6 weeks, 7 to 8 weeks, 9 to 10 weeks, and 11 to >12 weeks) and the number and

CONFIDENTIAL

percentage of subjects in each duration category. Treatment duration (days) will also be summarized using descriptive statistics (n, mean, SD, median, minimum, and maximum).

Percent of study drug compliance is defined as $\{(number\ of\ tablets\ dispensed - number\ of\ tablets\ returned) / (date\ of\ last\ dose - date\ of\ first\ dose + 1)\} \times 100\%$. If a value for the number of returned tablets is missing or the return date is missing, then 100% compliance will be assigned for each day up to the number of tablets dispensed or up to the date of return whichever is earlier.

Study medication compliance will be summarized by compliance category (<80%, 80 to 120%, and >120%) and the number of subjects in each compliance category. Study medication compliance will also be summarized as a continuous variable using descriptive statistics (n, mean, SD, median, minimum, and maximum).

All study drug administration and accountability data will be listed by study site and subject number. The following variables will be listed: subject identifier, visit number, first and last dose dates, medication identification number, date dispensed and returned, number of tablets dispensed and returned, and percent compliance.

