9.2 Monitoring Subject Treatment Compliance

Subjects will be required to bring study medication containers/unused study medication to each dispensing site visit. All supplies used to administer study drug to the subject will be recorded on the eCRFs.

If a subject is persistently noncompliant with study drug (eg, less than 70% compliant or greater than 125% compliant between visits), it may be appropriate to withdraw the subject from the study. All subjects should be reinstructed about the dosing requirement during study contacts. The authorized study personnel conducting the re-education must document the discussion in the subject source records.

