7.2 Analysis Sets

In this study, 3 kinds of analysis sets are defined: full analysis set (FAS), per protocol set (PPS) and safety analysis set.

The FAS, used for primary effectiveness analysis, will include all subjects who were enrolled in the treatment period and received at least 1 dose of the study drug and completed at least 1 GAS assessment post-Baseline. In FAS effectiveness summaries, subjects will be considered as vortioxetine-treated no matter what dose levels were received during the study.

A PPS will include all FAS subjects who had no major protocol violations. Subjects to be excluded from the PPS, whether due to protocol violations or noncompliance to the dosing prescribed by the treating physician, will be identified in the minutes of the subject evaluability assessment.

The Safety Analysis Set will include all subjects who were enrolled and received at least 1 dose of study medication. In safety summaries, all subjects will be analyzed as vortioxetine-treated.

The sponsor will verify the validity of the definitions of the analysis sets as well as the rules for handling data, with consulting a medical expert as needed. If necessary, the Handling Rules for Analysis Data will be supplemented with new handling rules that were not discussed at the planning stage. The Handling Rules for Analysis Data must be finalized prior to database lock.

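### SAP 7.7 fills missing tablet returns with 100% per day up to a cap; this may overstate compliance, and the amount imputed is never reported

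*SAP*

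**What the plan says.** SAP 7.7 defines percent compliance as tablets dispensed minus tablets returned, divided by the days from first to last dose inclusive. It then gives a missing-data rule. The trigger is "If a value for the number of returned tablets is missing or the return date is missing"; the imputed value is that "then 100% compliance will be assigned for each day up to the number of tablets dispensed"; and the limit continues "or up to the date of return whichever is earlier". The value is therefore 100% per day under a cap, not a flat 100% per subject.

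The result is reported in three bands (below 80%, 80 to 120%, above 120%) and as a continuous variable. On the population, the SAP states: "The summary of study drug exposure and compliance will be based on the safety analysis set". The planned listing shows tablets dispensed and returned, the dates and percent compliance, but no indicator that a value was imputed. No observed-only summary and no count of imputed subjects or intervals is specified.

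Two other places use the idea of compliance:
- SAP 7.2 allows exclusion from the per-protocol set (PPS) for "noncompliance to the dosing prescribed by the treating physician", to be identified in the minutes of the evaluability assessment. It gives no numeric cut-off and no reference to the SAP 7.7 percentage.
- Protocol 9.2 mentions subjects "less than 70% compliant or greater than 125% compliant between visits" as possible candidates for withdrawal.

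**The concern.** The rule replaces missing accountability with the target value. A subject lost to follow-up has by definition not come back to the clinic (Protocol 7.4), so the last bottle is the one most likely to be uncounted. If such subjects took fewer tablets than prescribed, mean compliance is too high and the below-80% band is under-counted. The table would not show how much of it was measured and how much was assumed.

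The trigger is also wider than it needs to be. The compliance formula uses tablets dispensed, tablets returned and the first and last dose dates. It does not use the return date. Yet a missing return date alone is enough to set a recorded count aside.

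At stake is a descriptive table and, if the evaluability review relies on the same percentage, who stays in the PPS.

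**Working it through.** The plan gives no expected compliance and no rate of missing returns, so there is no stated figure to reproduce. The check applies the SAP 7.7 rule to the planned schedule.

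**Inputs**
- One tablet daily, and for packaging "Each bottle contains 28 daily doses plus 7 extra tablets for a total of 35 tablets per bottle" (Protocol 8.1.1.1).
- Dispensing at Baseline, Week 2 and Week 6; return at Days 15, 43 and 85 (Protocol Appendix A). The intervals are 15 − 1 = 14, 43 − 15 = 28 and 85 − 43 = 42 days, 84 in all.
- Bottles per visit are not stated. Two cases are taken: one bottle at each visit, or two at Week 6.
- About 120 enrolled (Protocol 6.1) and 100 assumed to complete (Protocol 13.3, SAP 6.0). By subtraction, about 20 do not complete.
- Assumptions: 10 to 20 subjects with missing returns, and true compliance among them of 60% to 75%. Imputation is read interval by interval, with imputed days limited to the interval length.

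**Step 1. Value the rule assigns.** Imputed days = min(tablets dispensed, days to return).
- One bottle each visit: min(35, 14) + min(35, 28) + min(35, 42) = 14 + 28 + 35 = 77; 77/84 = 91.7%. The cap binds only in the last interval (35/42 = 83.3%).
- Two bottles at Week 6: 14 + 28 + 42 = 84; 84/84 = 100%.

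With every return missing, the subject falls in the 80 to 120% band either way.

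**Step 2. Change of band.** Suppose the first two intervals are fully taken and counted, half the tablets are taken in the last interval, and its count is missing.
- True: (14 + 28 + 21)/84 = 63/84 = 75%, below 80%.
- Tabulated: (14 + 28 + 35)/84 = 91.7%, or (14 + 28 + 42)/84 = 100%.

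**Step 3. Known count overwritten.** Take the same subject with one bottle dispensed at Week 6 and 35 − 21 = 14 tablets recorded as returned, but no return date. The formula gives the correct 75%. The rule, read literally, replaces it with 91.7%.

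**Step 4. Shift in the mean.** Shift = (k/120) × (imputed − true), for k affected subjects.

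| Imputed part | k = 10, true 75% | k = 20, true 60% |
|---|---|---|
| All intervals, at 100% | 10/120 × 25 = 2.1 points | 20/120 × 40 = 6.7 points |
| All intervals, at 91.7% | 10/120 × 16.7 = 1.4 points | 20/120 × 31.7 = 5.3 points |
| Last 42 of 84 days, at 100% | 0.5 × 2.1 = 1.0 point | 0.5 × 6.7 = 3.3 points |

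The last row assumes compliance is uniform over treatment.

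**Step 5. Direction.** The shift is zero if these subjects took every tablet, and negative if they took extra. With 10% of subjects affected at a true 110%, it is 0.10 × (100 − 110) = −1.0 point.

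**The case against.** Several points on the other side are sound.

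- **The rule has a purpose.** Counting a missing return as zero tablets returned would give 105/84 = 125% with one bottle per visit, or 140/84 = 166.7% with two at Week 6. The rule avoids those artificial values.
- **Non-completion is not a missing count.** Early-termination visits include drug return (Protocol 9.3.5 and Appendix A), and sites must account for all drug (Protocol 8.3). Twenty missing counts is an upper case.
- **Stopping early is not non-compliance here.** The denominator ends at the last dose, so days after discontinuation do not count.
- **Leaving non-returners out removes little bias.** Suppose 100 returners average 95% and 20 non-returners truly average 60%. The true mean is (100 × 95 + 20 × 60)/120 = 89.2%. The SAP rule gives (100 × 95 + 20 × 100)/120 = 95.8%, and observed-only gives 95.0%. The excess falls only from 6.7 to 5.8 points.

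These limit the size of the point and rule out stronger readings that a reader might infer:
- *That compliance is biased upward as a matter of fact.* The documents give neither the missing-return rate nor these subjects' compliance.
- *That about 20 of 120 subjects (16.7%) are forced out of the below-80% band.* Earlier recorded intervals still count. A subject at 50% through the first 42 days with the rest imputed in full is at (21 + 42)/84 = 75%, or (21 + 35)/84 = 66.7% under the one-bottle cap; both stay below 80%.
- *That non-returners cannot be excluded from the PPS.* SAP 7.2 does not tie the PPS to this percentage, Protocol 9.2 concerns possible withdrawal, and the listing lets a reviewer see that a count is absent.

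What the objection does not answer is that the table hides how much was imputed, and that a recorded count can be discarded for want of a date.

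**Conclusion.** The point holds as a minor one. The imputation may overstate compliance, can put a subject truly at 75% into the 80 to 120% band at 91.7% or 100%, and literally overrides a known count when only the return date is missing.

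Direction and size are conditional. The 2.1 to 6.7 point rise in the mean rests on the assumed number affected and their assumed true compliance, with all intervals imputed at 100%. It is about half that if only the last interval is missing, and smaller again if the one-bottle cap applies.

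The consequence is confined to a descriptive safety-set table and, possibly, the PPS review. SAP 7.8 runs all efficacy analyses on the FAS, so neither the primary endpoint nor the secondary results change.

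**What to change.** Amend SAP 7.7 as follows:

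1. Use the recorded returned count whenever it exists, including when the return date is missing.
2. Report the number of subjects and of dispensing intervals with an imputed value.
3. Make the main compliance summary the one over intervals with recorded counts, and show the 100% rule only as a labelled best-case row.
4. Flag imputed values in the accountability listing.
5. State in SAP 7.2 that an imputed value is not evidence of compliance when PPS membership is decided.

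The cost is SAP wording and one or two table rows. The observed-only row will have a smaller n and does not by itself remove bias from non-returners, which is why the count in item 2 must stand beside it. The reported compliance figure may be slightly less favourable.
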